9 ADVERSE EVENTS

9.1 Adverse Event Definitions

An adverse event (AE), an adverse drug reaction (ADR), and a serious adverse event (SAE) are defined according to ICH Guideline E2A (ICH 1994).

An AE is any untoward medical occurrence in a subject administered the IMP and which may or may not have a causal relationship with this IMP. An AE can therefore be any unfavorable and unintended sign (e.g. a significant abnormal laboratory finding, symptom, or disease temporally associated with the use of the IMP, whether or not considered related to the IMP.

An ADR is any noxious and unintended response to an IMP related to any dose of the IMP.

An SAE is any untoward medical occurrence that at any dose:

- Results in death
- Is life-threatening (this refers to an event in which the subject was at risk of death at the time of the event; it does not refer to an event that hypothetically might have caused death if it was more severe)
- Requires in-patient hospitalisation or prolongation of existing hospitalisation
- Results in persistent or significant disability or incapacity
- Is a congenital anomaly or birth defect

Vicore Pharma AB Version: 2.0 Trial ID: VP-C21-006 Date: 14-Aug-2020

• Is judged medically important (this refers to an event that may not be immediately lifethreatening or result in death or hospitalisation, but may jeopardise the subject or may require intervention to prevent one of the other outcomes listed)

A non-SAE is any AE that does not meet the definition of an SAE.

The following will not be considered an AE:

- Pre-planned procedure (documented at Visit 1) unless the condition for which the procedure was planned has worsened from the first trial related activity after the subject has signed the informed consent form
- Concomitant illness identified as a result of screening procedures. However, if symptoms are worsened and/or become serious as defined in Section 9.1, this must be reported as a SAE.

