### 6.11.1 Adverse Events

Adverse events will be coded using the latest MedDRA dictionary version. The version used will be indicated in the data summaries and listings.

A treatment-emergent adverse event (TEAE) is defined as an AE that started on or after the start of the administration study treatment. If adverse event dates are incomplete and it is not clear whether the adverse event was treatment-emergent, it will be assumed to be treatment-emergent.

The relationship with study treatment will be entered in to the eCRF (related/not related). If the TEAE has a missing relationship it is assumed to be related to the study treatment for analysis purposes.

A summary table will present the following:

- TEAEs (events and subjects).
- Serious TEAEs (events and subjects).
- Serious study treatment-related TEAEs (events and subjects).
- TEAEs by severity (mild/moderate/severe) (events and subjects).
- TEAEs by relationship to study treatment (events and subjects).
- TEAEs leading to withdrawal from study (subjects only).
- TEAEs leading to discontinuation of study treatment (subjects only).
- Study treatment-related TEAEs leading to discontinuation of study treatment (subjects only).
- TEAEs leading to death (subjects only).

In the above summaries, if a subject experienced more than one TEAE, the subject will be counted once using the most related event for the “by relationship to study treatment” and “related to study treatment” summaries and at the worst severity for the “by severity” summary.

The following tables will be presented:

- TEAEs by SOC and PT.
- TEAEs by SOC, PT and severity.
- TEAEs by SOC, PT and relationship to study treatment.
- TEAEs leading to treatment withdrawal by SOC and PT.
- Serious TEAEs by SOC and PT.

For all of the above, SOC and PT will be presented in decreasing frequency of the total number of subjects with TEAEs.

Further details of the above five tables are given below:

1. If a subject experienced more than one TEAE, the subject will be counted once for each SOC and once for each PT.
2. If a subject experienced more than one TEAE, the subject will be counted once for each SOC and once for each PT at the worst severity.
3. If a subject experienced more than one TEAE, the subject will be counted once for each SOC and once for each PT using the most related event.

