8.2.7 Safety Laboratory Parameters

Safety laboratory parameters which are to be taken at every visit except Visit 9 (end-of-trial):

Vicore Pharma AB Version: 2.0 Trial ID: VP-C21-006 Date: 14-Aug-2020

• Haematology: haemoglobin (Hb), haematocrit (erythrocyte volume fraction), platelet count (thrombocyte particle concentration [TPC]), leucocyte count, mean corpuscular volume (MCV), white blood cells with differential count

- Biochemistry: albumin, alanine transferase (ALT), aspartate aminotransferase (AST), alkaline phosphatase (ALP), bilirubin, blood urea nitrogen (BUN), calcium, creatinine, glucose, potassium, sodium
- Urinalysis: dipstick for bilirubin, glucose, ketones, protein, specific gravity, urobilinogen, and pH

Any laboratory abnormality, judged by the Investigator to be a clinically relevant worsening since Visit 1, should be reported as an adverse event if the laboratory abnormality requires clinical intervention or further investigation, unless the laboratory abnormality is associated with an already reported event.

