9.2 Adverse Event Assessment Definitions

9.2.1 Severity

The Investigator should assess the severity of all AEs according to the following definitions:

- Mild: awareness of sign or symptom, but easily tolerated (acceptable).
- Moderate: discomfort to interfere with usual activities (disturbing).
- Severe: incapacity to work or to perform usual activities (unacceptable).

Note the distinction between seriousness and severity: The term severe is used to describe the intensity of the event and a severe event is not necessarily serious. The seriousness criteria serve as a guide for defining regulatory reporting obligations.

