9.3 Reporting of Adverse Events

All events meeting the definition of an AE must be reported in the period from the subject has signed the informed consent form until the end-of-trial participation (Visit 9).

At each visit the subject will be asked about AEs in an objective manner, e.g.: "Have you experienced any problems since the last visit?"

Only medically qualified personnel (Investigators) must assess AEs.

AEs must be reported on the AE form. In the eCRF the diagnosis should be recorded, if available. If no diagnosis is available each sign and symptom should be recorded as individual AEs.

SAEs, in addition, must be reported within 24 hours of obtaining knowledge of the event. The information to be reported will include assessment of severity, causal relationship to IMP or trial procedures, action taken, outcome, and a narrative description of the course of the event. Additional information may be subsequently provided.

The SAE form and all other relevant documents supporting the reported SAE (e.g. diagnostic procedures, hospital records, autopsy reports) must be faxed or scanned/emailed to the Sponsor or Sponsor's designee.

The independent ethics committees (IEC) and regulatory authorities will be notified of SAEs according to current regulation and local requirements.

All suspected unexpected serious adverse reactions (SUSARs) are subject to expedited reporting to regulatory authorities. Pharmacovigilance will unblind such cases prior to reporting.

Investigators, the Sponsor and local IECs (if applicable) will remain blinded.

Vicore Pharma AB Version: 2.0 Trial ID: VP-C21-006 Date: 14-Aug-2020

The expectedness of a SUSAR will be assessed against the reference safety information. Any SUSARs will be reported by the clinical research organisation (CRO) to the relevant competent authority. SUSARS will also be reported to the IEC by the site/CRO. Fatal and life threatening SUSARs will be reported as soon as possible and no later than seven calendar days from the date of first knowledge of the event. Relevant follow-up information will subsequently be expedited within an additional eight days. All other SUSARs will be expedited no later than 15 calendar days of first knowledge of the event.

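### Protocol 9.1, read literally, makes a non-serious worsening of a screening-identified illness an SAE, against the section's own SAE definition

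*Combined protocol and SAP*

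**What the plan says.** Protocol Section 9.1 (Adverse Event Definitions) contains three statements that bear on this point.

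- The SAE definition: "An SAE is any untoward medical occurrence that at any dose" leads to one of six outcomes (death, threat to life, hospitalisation or its prolongation, disability, congenital anomaly, or medical importance).
- Its complement: "A non-SAE is any AE that does not meet the definition of an SAE".
- A list of things that do not count as AEs. The second item is "Concomitant illness identified as a result of screening procedures", followed directly by: "However, if symptoms are worsened and/or become serious as defined in Section 9.1, this must be reported as a SAE".

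Elsewhere, Section 8.2.7 says that a clinically relevant laboratory worsening since Visit 1 "should be reported as an adverse event if the laboratory abnormality requires clinical intervention or further investigation". Section 9.2.1 separates intensity from seriousness: "a severe event is not necessarily serious". Section 9.3 attaches a further duty to the SAE label: "SAEs, in addition, must be reported" within 24 hours of the site learning of the event.

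On the analysis side, SAP Section 6.11.1 counts serious TEAEs and treatment-related serious TEAEs in the overview table, and it also plans a table of "Serious TEAEs by SOC and PT".

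**The concern.** The sentence on screening-identified illness joins two triggers with *and/or*. On the plain wording either one is enough, so worsening alone makes the event an SAE even if it is mild and meets none of the six criteria. The same section classes such an event as a non-SAE.

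Safety profile is a secondary objective and AEs are a secondary endpoint. An SAE label starts the 24-hour report and, if the event is judged related and unexpected, expedited reporting with unblinding by pharmacovigilance. It also puts the event in line for the serious-TEAE tables. Neither document plans a check of reported SAEs against the six criteria, so a misclassification at site would carry through to the report. SAP Section 2.3 foresees one UK site and up to 12 sites in India, so different readings of one unclear sentence are plausible.

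**Working it through.** No figure in the plan depends on this point, so the check is mainly a comparison of texts.

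**Step 1: apply each reading to the same event.** Take an illness found at screening that worsens after consent.

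| Event | *And/or* read literally | Seriousness required for both triggers |
|---|---|---|
| Worsening that meets a seriousness criterion | SAE | SAE |
| Worsening that meets none | SAE, contrary to the SAE and non-SAE definitions | Not an SAE; the bullet names no AE route |

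The readings agree on serious worsening and part on non-serious worsening. Under neither does the bullet itself give the usual result, which is an AE raised to an SAE only when a criterion is met.

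**Step 2: compare with how the protocol treats worsening elsewhere.**

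- The neighbouring item in the same list, on pre-planned procedures, lets worsening of the underlying condition lift the exclusion. The event then becomes an AE, with no automatic step to SAE.
- Section 8.2.7 makes a clinically relevant laboratory worsening an AE when it needs intervention or investigation.
- Section 9.2.1 warns against equating intensity with seriousness.

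All three point the same way, and the sentence at issue is the exception.

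**Step 3: direction of the effect on the tables.** The documents give no SAE rate and no rate of such worsenings, so the following uses assumed values only to show direction. Let p be the true SAE proportion in an arm and q the proportion of subjects with a non-serious worsening filed as an SAE, equal in both arms and independent of true SAEs. Then:

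- observed proportion = 1 − (1 − p)(1 − q)
- observed difference = (p₂ − p₁)(1 − q)

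For p₁ = 5%, p₂ = 10% and q = 2%: 1 − 0.95 × 0.98 = 6.9%, 1 − 0.90 × 0.98 = 11.8%, ratio 1.71, difference 4.9 points. The other cases follow in the same way:

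| True rates (assumed) | Ratio at q = 0 | q = 2% | q = 5% | q = 10% | Difference, q = 0 to q = 10% |
|---|---|---|---|---|---|
| 5% vs 10% | 2.00 | 1.71 | 1.49 | 1.31 | 5.0 to 4.5 points |
| 5% vs 15% | 3.00 | 2.42 | 1.97 | 1.62 | 10.0 to 9.0 points |
| 10% vs 20% | 2.00 | 1.83 | 1.66 | 1.47 | 10.0 to 9.0 points |

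Both arms' counts rise, the ratio moves toward 1, and the absolute difference changes little. The values of q are not estimates.

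**The case against.** Several points against the concern have force.

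- **The literal reading is not the only one.** The sentence refers back to Section 9.1, and that reference can be taken to govern both triggers. This stands. A reader might infer that the protocol unequivocally orders every worsening to be filed as an SAE; the text supports that as its plain wording, not as its only meaning. The alternative still leaves the bullet without an explicit AE route.
- **Non-serious worsenings need not be lost.** A reader might infer that they go unreported under the alternative reading. The documents do not support that as a general claim. Section 9.1 defines an AE as any untoward medical occurrence, Section 9.3 requires all such events to be reported, and Section 8.2.7 covers laboratory worsening that needs intervention or investigation. A site could use these routes. Under-reporting is a possible outcome of one reading, not a stated rule.
- **The scope is narrow.** The bullet covers illness found through screening procedures, not known history. COVID-19 itself appears to lie outside it, since Section 8.2.2 distinguishes the disease under study from concomitant illnesses. The exclusion criteria remove many candidate conditions, and participation lasts about three weeks. This stands.
- **Some events may never reach the tables.** SAP Section 6.11.1 defines a TEAE by its start relative to first treatment, with no clause for worsening. An illness recorded with its original onset date, or one that worsens before dosing, stays out. This stands, and it also means that what is tabulated depends on how the site dates the event.
- **Randomisation and blinding protect the comparison.** Differences between sites in reading the sentence are not tied to arm, the AE tables carry no test, and the literal reading errs toward over-reporting. This removes any expected directional bias, but not the noise or the needless expedited reports.

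**Conclusion.** The inconsistency is real and lies within one section. As worded, the reporting rule produces a wrong classification if a site follows it literally, and different classifications if sites read it differently. It is worth correcting because it is an operative instruction that feeds expedited reporting and the serious-TEAE tables.

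Its size should be stated modestly. The number of affected events is probably small, given the narrow scope, and cannot be estimated from the documents. A reader might infer that misfiled events could match the true SAEs in number, or could tilt the safety comparison toward one arm. No rate in the documents supports the first, and blinded randomisation argues against the second. The expected effect is inflated counts and a weaker relative contrast, on the assumption that such worsenings are about equally frequent in both arms. The CRP endpoint, the significance level and the sample size are unaffected.

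**What to change.** Replace the sentence in protocol Section 9.1 with:

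> If such an illness worsens after informed consent, the worsening must be reported as an AE; it must be reported as an SAE only if it meets a seriousness criterion in Section 9.1.

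This brings the bullet into line with the definitions above it, the pre-planned-procedure item and Section 8.2.7, and removes the need for sites to choose a reading. It can be issued by amendment or as a memo to sites.

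Also re-check any SAE forms already filed for worsening of a screening-identified illness against the six criteria. Under Section 7.6 allocation stays undisclosed until the database is locked, so doing this before lock keeps it blind to treatment. The cost is one sentence and, at most, a review of the forms concerned. No treatment or visit procedure changes.

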9.2 Adverse Event Assessment Definitions

9.2.1 Severity

The Investigator should assess the severity of all AEs according to the following definitions:

- Mild: awareness of sign or symptom, but easily tolerated (acceptable).
- Moderate: discomfort to interfere with usual activities (disturbing).
- Severe: incapacity to work or to perform usual activities (unacceptable).

Note the distinction between seriousness and severity: The term severe is used to describe the intensity of the event and a severe event is not necessarily serious. The seriousness criteria serve as a guide for defining regulatory reporting obligations.

9.2.2 Relationship to IMP

Assessment of causality is based on the following considerations: associative connections (time and/or place), pharmacological explanations, previous knowledge of the drug, presence of characteristic clinical or pathological phenomena, exclusion of other causes, and/or absence of alternative explanations.

The Investigator will be asked to assess causal relationship to the IMP according to the following classifications:

Related:

• Time relationship exists; and previous knowledge of the trial product supports a causal relationship although another cause cannot be ruled out; and/or improvement on dechallenge or dose reduction has occurred (if performed); and/or recurrence of symptoms on rechallenge has occurred (if performed); and/or a specific laboratory test supports a causal relationship

Vicore Pharma AB Version: 2.0 Trial ID: VP-C21-006 Date: 14-Aug-2020

Not related:

• No time relationship between administration of the trial product and occurrence or worsening of the AE exists; and/or another cause is confirmed and no indication for involvement of the trial product in the occurrence/worsening of the AE exists. The alternative, most likely other cause(s) should be indicated

9.2.3 Outcome

The Investigator will be asked to record the most appropriate outcome of the following:

- Recovered/resolved
- Recovering/resolving
- Not recovered/not resolved
- Recovered/resolved with sequelae
- Fatal
- Unknown

9.3 Reporting of Adverse Events

All events meeting the definition of an AE must be reported in the period from the subject has signed the informed consent form until the end-of-trial participation (Visit 9).

At each visit the subject will be asked about AEs in an objective manner, e.g.: "Have you experienced any problems since the last visit?"

Only medically qualified personnel (Investigators) must assess AEs.

AEs must be reported on the AE form. In the eCRF the diagnosis should be recorded, if available. If no diagnosis is available each sign and symptom should be recorded as individual AEs.

SAEs, in addition, must be reported within 24 hours of obtaining knowledge of the event. The information to be reported will include assessment of severity, causal relationship to IMP or trial procedures, action taken, outcome, and a narrative description of the course of the event. Additional information may be subsequently provided.

The SAE form and all other relevant documents supporting the reported SAE (e.g. diagnostic procedures, hospital records, autopsy reports) must be faxed or scanned/emailed to the Sponsor or Sponsor's designee.

The independent ethics committees (IEC) and regulatory authorities will be notified of SAEs according to current regulation and local requirements.

All suspected unexpected serious adverse reactions (SUSARs) are subject to expedited reporting to regulatory authorities. Pharmacovigilance will unblind such cases prior to reporting.

Investigators, the Sponsor and local IECs (if applicable) will remain blinded.

Vicore Pharma AB Version: 2.0 Trial ID: VP-C21-006 Date: 14-Aug-2020

The expectedness of a SUSAR will be assessed against the reference safety information. Any SUSARs will be reported by the clinical research organisation (CRO) to the relevant competent authority. SUSARS will also be reported to the IEC by the site/CRO. Fatal and life threatening SUSARs will be reported as soon as possible and no later than seven calendar days from the date of first knowledge of the event. Relevant follow-up information will subsequently be expedited within an additional eight days. All other SUSARs will be expedited no later than 15 calendar days of first knowledge of the event.

9.4 Follow-up on Adverse Events

All AEs should be followed until they are resolved or the subject's participation in the trial ends, whichever comes first.

SAEs and severe, non-serious AEs considered related to IMP should be followed on a regular basis according to the investigator's clinical judgment until a final outcome has been established.

9.5 Pregnancies

Any pregnancy that occurs during trial participation must be reported and administration of IMP must be terminated immediately. A pregnancy must be reported immediately to Sponsor or designee. The pregnancy must be followed up to determine outcome (including premature termination) and status of mother and infant. Pregnancy complications and elective terminations for medical reasons must be reported as AEs or SAEs, as applicable. Spontaneous abortion must be reported as an SAE.

In addition, the Investigator must attempt to collect pregnancy information on any female partners of male trial participants who become pregnant while the participant is enrolled in the trial. Pregnancy information must be reported to Sponsor as described above.

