5.3 Restrictions During the Trial

5.3.1 Contraception Requirements

Women of child bearing potential must practice abstinence (if that is their preferred lifestyle) from Visit 1 to Visit 9, or must agree to use a highly effective method of contraception with a failure rate of <1% to prevent pregnancy (combined [oestrogen and progestogen containing] hormonal contraception associated with inhibition of ovulation [oral, intravaginal, transdermal], progestogen-only hormonal contraception associated with inhibition of ovulation [oral, injectable, implantable], intrauterine device or intrauterine hormone-releasing system) from at least 4 weeks prior to first IMP administration to 4 weeks after last IMP administration. Their male partner must agree to use a condom during the same time frame, unless he has had a demonstrated successful vasectomy more than 6 months prior to first IMP administration.

Males should use condom and their female partner of child-bearing potential must use a contraceptive method with a failure rate of <1% to prevent pregnancy (see above) and drug exposure of a partner and refrain from donating sperm from the date of dosing until 3 months after the last IMP administration.

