6.5.4 End-of-Trial (Visit 9)

Visit 9 is performed for all randomised subjects 7-10 days after the last IMP administration and may be performed as a telephone contact.

The following procedures are performed:

- Concomitant medication
- Date of discharge
- Use of supplemental O₂
- Use of mechanical invasive and non-invasive mechanical ventilation
- Adverse events

If a subject is prematurely withdrawn from IMP, Visit 9 must be performed 7-10 days after last IMP dose (see Section 5.4.1).

Vicore Pharma AB Version: 2.0 Trial ID: VP-C21-006 Date: 14-Aug-2020

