8.2.3 Pregnancy Test

Women of childbearing potential will undergo pregnancy tests (urine dip-sticks) at Visit 1 and Visit 8 (or at the withdrawal assessments if the subject is withdrawn prematurely). If the urine pregnancy test is positive, a blood pregnancy test will be performed to confirm positive pregnancy.¹⁾

1) Women of non-childbearing potential are defined as pre-menopausal females who are sterilised (tubal ligation or permanent bilateral occlusion of fallopian tubes); or post-menopausal defined as 12 months of amenorrhea).

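### Pregnancy reporting ends at Visit 9 and so covers only 7–10 of the 28 post-dose contraception days for women using a method, and 7–10 of about 90 for partners of men

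*Combined protocol and SAP*

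**What the plan says.** **Reporting rule (Protocol 9.5).** For participants: "Any pregnancy that occurs during trial participation must be reported and administration of IMP must be terminated immediately". For men, the investigator must try to collect information on "female partners of male trial participants who become pregnant while the participant is enrolled in the trial". A pregnancy, once reported, is followed to its outcome, with no stop at Visit 9.

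**When participation ends.** Section 9.5 gives no date. Section 9.3 runs adverse event reporting "until the end-of-trial participation (Visit 9"), and Section 8.2.1 has the same limit. On timing, Section 6.5.4 says: "Visit 9 is performed for all randomised subjects 7-10 days after the last IMP administration and may be performed as a telephone contact". Its procedure list contains no pregnancy test and no pregnancy question.

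**Contraception rule (Protocol 5.3.1).** Women using a contraceptive method must do so "from at least 4 weeks prior to first IMP administration to 4 weeks after last IMP administration". Women who choose abstinence are covered from Visit 1 to Visit 9 only. The sentence for men covers condoms, contraception by the partner and sperm donation, and ends with the instruction to "refrain from donating sperm from the date of dosing until 3 months after the last IMP administration".

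**Testing (Protocol 8.2.3).** "Women of childbearing potential will undergo pregnancy tests (urine dip-sticks) at Visit 1 and Visit 8", with the second test moved to the withdrawal assessment if the subject stops early. SAP 6.11.7 lists details of these tests.

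**The concern.** The protocol asks participants to avoid pregnancy for a stated time after the last dose, but it stops asking about pregnancy well before that time is over. Nothing in the available text requires a pregnancy that begins between Visit 9 and the end of the contraception period to be reported. For one that begins earlier but is not yet recognised, nothing prompts anyone to look for it or mention it after Visit 8.

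What is at stake is safety information. Section 3.3 describes the target receptor as expressed mainly in embryonic tissue, and Section 3.5 puts prior human exposure at 83 subjects with at least one dose. A trial report showing no pregnancies could reflect the end of collection rather than the absence of events. Alpha, power and the primary analysis are not involved.

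**Working it through.** **Inputs**
- Screening up to 3 days, treatment 7 days, Visit 9 at 7–10 days after the last dose (Protocol 6.1, 6.5.4).
- Women using a method: 4 weeks = 28 days after the last dose (5.3.1).
- Men and partners: 3 months after the last dose, taken as 90–92 days (5.3.1; the day count is an assumption).

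**Plan's own figure.** Maximum duration per subject = 3 + 7 + 10 = 20 days, which agrees with the approximately 3 weeks in Section 6.1.

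**Post-dose coverage** = (days from last dose to Visit 9) / (days in the contraception period).

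| Group | Covered | Share | Not covered |
|---|---|---|---|
| Women using a method | 7–10 of 28 | 7/28 = 25% to 10/28 = 36% | 28 − 10 = 18 to 28 − 7 = 21 days |
| Partners of men | 7–10 of 90–92 | 7/92 = 8% to 10/90 = 11% | 90 − 10 = 80 to 92 − 7 = 85 days |

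Women choosing abstinence have no gap against their own period, because that period also ends at Visit 9.

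**Counting from the first dose**, by date of conception, the 7 treatment days are added to both parts:
- Women using a method: (7 + 7)/(7 + 28) = 14/35 = 40% to (7 + 10)/35 = 17/35 = 49%.
- Partners of men: 14/99 = 14% to 17/97 = 18%.

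**By date of recognition.** This needs a lag L from conception to recognition, which the documents do not give. Conception days from Day 1 that could be recognised by Visit 9 = max(0, 7 + v − L), with v = 7 to 10:

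| Assumed L (days) | Conception days recognisable by Visit 9 | Share of the women's 35 days |
|---|---|---|
| 7 | 7–10 | 20–29% |
| 10 | 4–7 | 11–20% |
| 14 | 0–3 | 0–9% |
| 21 | 0 | 0% |

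At any L of 7 days or more, the Visit 8 test finds no conception from Day 1 onward, since max(0, 7 − L) = 0. It can find one that preceded dosing and was missed at Visit 1.

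**Early stopping does not close the gap.** Discharge ends study treatment (5.4.1), and Section 3.8 expects patients generally to be discharged or moved to intensive care within 7 days. A subject discharged on Day 3 would be tested around Day 3 and would leave the reporting window on about Days 10–13. The post-dose coverage stays at 7–10 days.

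**Inconsistency inside Section 5.3.1.** The abstinence option and the contraceptive option for women end at different times. For men, the 3-month limit closes a long sentence. It may govern everything in that sentence or sperm donation alone; if only sperm donation, partner contraception has no stated end.

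**The case against.** A reader might infer that almost no exposed pregnancy can be captured. The documents do not support that. By conception date, 40–49% of the women's period and 14–18% of the men's lie inside the window. The stronger statement needs an assumed recognition lag of about 14 days or more.

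A reader might also infer that later-recognised pregnancies are barred from reporting or left without follow-up. Section 9.5 ties the duty to when the pregnancy occurs and sets no deadline for learning of it. A conception during dosing that is recognised after Visit 9 can be read as still reportable, and then followed to outcome. This stands; the weakness there is that nothing prompts the report.

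Other points on that side:
- The periods in 5.3.1 are contraception requirements, not stated exposure periods. C21 was measurable in plasma only until 4–6 hours after each dose (3.8), so the uncovered days are a precautionary margin. This stands. It limits the seriousness but does not explain why the two sections differ.
- Conception during the treatment days is unlikely in inpatients who are under contraception or abstinence rules. This is fair, but the uncovered days come after Visit 9, when many subjects will be at home.
- The general adverse event question at Visit 9 might bring up a pregnancy. It might, but it cannot reach one that begins later.
- Consent pages are not available for this review, and an instruction to report later pregnancies could be there. Its absence from the participant information cannot be established. Even so, Section 9.5 itself would not make such a pregnancy reportable.

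**Conclusion.** The mismatch is real and modest. As written, pregnancy reporting leaves 18–21 of the 28 post-dose days uncovered for women using a contraceptive method, and about 80–85 of 90–92 days for partners of men. No test is scheduled after Visit 8 or withdrawal, and Visit 9 has no pregnancy question. Sections 5.3.1 and 9.5 must be reconciled, and 5.3.1 must also be made consistent within itself.

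This rests on three readings: that participation in 9.5 ends at Visit 9, as the adverse event sections say; that 3 months is 90–92 days; and that the 3-month limit applies to partner contraception as well as sperm donation. If it applies to sperm donation only, the figure for partners has no firm denominator. The documents give no basis for an expected number of pregnancies, so the size is stated in days of coverage, not in missed cases. The point is worth acting on because the remedy is cheap.

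**What to change.** 1. Reconcile Sections 5.3.1 and 9.5. In 5.3.1, settle whether the two options for women are meant to end at different times, and what the 3-month limit governs. Which periods are right is for the sponsor to decide.
2. In 9.5, keep trial participation as the start of pregnancy reporting. Starting at the first dose could drop pregnancies that begin between Visit 1 and dosing, which are now covered. Extend the end to one explicit date for women and one for partners of men, consistent with the reconciled 5.3.1.
3. State that a pregnancy beginning in that window is reportable whenever it is recognised. The existing follow-up to outcome then applies.
4. Add a line to the Visit 9 procedures (6.5.4) asking participants to tell the site of a later pregnancy.

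No extra visit or test is needed. If the present periods stand, reporting runs 18–21 days longer for women using a method and about 80–85 days longer for partners. Sites would accept passive reports for up to about 3 months after the last dose. Some may arrive after database lock and be held in the safety database only, so the trial report may still not show every case.
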